negative-sense RNA that encode viral proteins (2). Vaccines against this virus have traditionally relied on inducing antibodies that protect against viral infection by binding to the HA surface glycoprotein and neutralizing virions. However, the rapid accumulation of point mutations in both the HA and NA proteins allow this virus to drift and escape neutralization, resulting in yearly epidemics despite the availability of influenza vaccines (1, 3). In addition, the segmented genome of influenza virus allows sporadic reassortment to occur, which can result in antigenic shift and creation of a strain against which the population has little preexisting immunity. Such a reassortment event occurred in 2009, when a novel swine-origin influenza virus emerged and spread globally, resulting in the first influenza pandemic of the 21st century (4, 5).

It is estimated that 20% of children become infected with influenza yearly, with increasing rates during severe epidemics (6, 7). In addition to providing a reservoir for community infection, childhood influenza infection results in a substantial number of outpatient and emergency room visits and can be associated with significant morbidity, including viral or secondary bacterial pneumonia (6-8). Hospitalization is highest in the very young (estimated at 4.5 per 1000 children 0 to 5 months old) (8), with overall childhood influenza-related mortality estimated at 0.21 deaths per 100,000 children (9). While annual influenza immunization is the most effective method to prevent infection, the influenza vaccine is suboptimal in children (10-12). Some evidence suggests that LAIV may induce broader, more protective immunity in the young (11, 13-16), however recently presented data demonstrated that LAIV failed to protect against H1N1 strains in the 2013-14 influenza season. Further, LAIV is not yet approved for use under the age of 2 due to concerns about the precipitation of wheezing (17, 18). As IIV is universally recommended in the USA beginning at 6 months of age (18, 19), increasing numbers of children are first exposed to influenza via IIV.

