Major strides in understanding the protective immune response to influenza have been made in recent years. Natural influenza infection stimulates vigorous inflammation with activation of multiple pattern recognition receptors. This leads to a robust innate immune response characterized by production of antiviral cytokines such as interferons that both limit early viral replication and instruct developing adaptive immunity (1, 20-23). As the infection progresses, viral replication results in abundant intracellular antigen that can be processed and presented to activate the adaptive immune response (1, 23). CD4 T cells have a multifaceted role in combating infection, providing help to promote B cell isotype switching and affinity maturation, CD8 T cell memory generation, and directly participating in viral clearance through the independent secretion of antiviral cytokines and direct, cell-mediated cytotoxicity (1, 3, 23-33). Additionally, CD8 T cells are activated and home to respiratory sites to eliminate infected cells (1, 3, 23, 28, 29) and antigen-specific B cells secrete high affinity, neutralizing antibodies that are able to provide strain-specific sterilizing immunity from future infection (1, 23, 34-37). While neutralizing antibody is thought of as the major correlate of protection (34-37), cellular immunity is increasingly recognized as important in protecting from severe disease (38-41). As T cells can recognize epitopes from conserved internal viral proteins (42-46), this protection can be very important in years when antigenic drift leads to a poor vaccine match or a pandemic influenza strain emerges.

In contrast to the robust response that develops following influenza infection, the immune response generated on vaccination with IIV is characterized by weak inflammatory signaling. These vaccines are produced by chemical inactivation of the H1N1, H3N2, and influenza B viral strains predicted to be circulating, with disruption and purification of the surface glycoproteins (HA and NA) (47-49). Vaccine is solely quantified based on the content of the HA protein and generally contains variable levels of NA, small amounts of internal virion proteins including NP, and only trace amounts of innate immune activators such as viral RNA (47, 50-52). This vaccine is delivered intramuscularly without the addition of an adjuvant in the USA (50-52). While IIV stimulates antibody (53-59) and CD4 T cell responses (59-63), little CD8 T cell immunity

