2. STUDY DESIGN:

2.1: Overview:

This study will be conducted as a single center, prospective, open-label evaluation of different methods of priming on the anti-influenza CD4 T cell and antibody response in young children. It is anticipated that this study will last 3 years, with approximately 1 year of follow up for each subject. The study objectives are to evaluate the specificity and functional potential of the CD4 T cell response and the quantity, breadth and avidity of the neutralizing antibody response following either influenza infection or receipt of different types of licensed influenza vaccine as follows:

- Primary objective: To comprehensively evaluate the specificity and functional potential of CD4 T cell responses on a single cell level using intracellular cytokine staining following restimulation with pools of HA and NP peptides

Secondary objectives will include:

- To assess the full spectrum of antigen-specific CD4 T cell cytokine and chemokine production using multiplex cytokine assays
- To perform in depth characterization of the specificity of the CD4 T cell response following influenza vaccination or infection by Elispot assay
- To evaluate the humoral immune response that develops in response to infection or administration of the LAIV or IIV vaccines
- To determine the frequency of HA-specific memory B cells established using these priming conditions
- To determine the influence of the CD4 T cell response on the breadth and avidity of the post-vaccination antibody response using arrayed imaging reflectometry to rapidly quantify antibody levels against multiple HA proteins, microneutralization assays to quantify neutralizing antibody titers against different viral strains, and enzyme linked immunosorbent assays to determine HA antibody avidity and quantify stalk reactive antibody

[figure not shown]

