The second cohort of children will be infants between 3 and 12 months of age who will be enrolled to investigate how the primary CD4 T cell response that develops following IIV administration differs from that established after natural influenza infection. Infants who receive vaccine in this cohort will be at least 6 months of age and will be enrolled in the fall before influenza begins to circulate in the community. Infants between 3 and 12 months of age who contract a natural influenza infection before any doses of vaccine are administered will be eligible for the natural infection arm of this cohort. Both of these infant groups will have blood drawn and a nasal wash obtained on study entry and at days 10 (+ 4d/- 2d) and 24 (+/- 4d) post-vaccination and then will be followed to the subsequent influenza season and rechallenged with IIV, with blood draws and nasal washes again completed pre-vaccination and at days 10 (+ 4d/- 2d) and 24 (+/- 4d) post-vaccination (Figure 3). Children who test positive for influenza will be allowed treatment with oseltamivir as recommended by the CDC (73). To accomplish this, the rapid influenza test result will be provided to the child's pediatrician, who will then coordinate treatment of the child.

Figure 3

[figure not shown]

Figure 3: Experimental schematic to determine whether the method of initial priming differentially poises subjects to respond to future influenza encounters. Subjects that receive LAIV, IIV, or that are naturally infected with influenza will have CD4 T cell and antibody responses examined at enrollment and at days 10 and 24 post vaccination. Cohort 1 contains children approximately 24-36 months of age. Cohort 2A contains infants 6-12 months of age in their first influenza season, while cohort 2B contains infants 3-12 months of age. All enrolled subjects will be followed longitudinally for a year and then will be revaccinated with IIV. CD4 T cell responses, antibody response, and transcriptional profiles will be examined prior to revaccination and at days 10 and 24 post vaccination.

2.2: Rationale for Study Design:

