3. CHARACTERISTICS OF THE RESEARCH POPULATION

3.1: Subject Characteristics

a. Number of Subjects: It is anticipated that this study will enroll a total of approximately 180 subjects. This includes 60 children between the ages of 24 and 35 months in the first cohort. These children will be divided equally into two groups of 30, with one group receiving IIV and the other receiving LAIV as described above. We expect to screen up to 120 subjects into the second cohort, of whom 45 will be enrolled in the full study and evaluable. This will include 30 children between the ages of 6 months and 1 year that will receive IIV and 15 children between the ages of 3 months and 1 year who become naturally infected with influenza virus. However, in order to enroll these 15 naturally infected children, we anticipate having to screen up to 90 children with signs of influenza like illness during the height of seasonal influenza circulation, as only a small number of these children will have respiratory infections as a result of influenza virus infection.

b. Gender and Age of Subjects: It is anticipated that there will be an approximately equal distribution of males and females enrolled. This will include 60 children between the ages of 24 and 35 months in the first cohort and up to 120 children between the ages of 3 months and 1 year in the second cohort, of whom 45 will be evaluable.

c. Racial and Ethnic Origin: It is anticipated that the demographic distribution of enrollment will approximately resemble that of the City of Rochester, which is about 40% Caucasian, 40% African-American, 15% Hispanic, and 5% other. No subject will be excluded because of their racial or ethnic origin.

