Infants between the ages of 6 months and 1 year of age receiving IIV before influenza reaches epidemic levels in the community will be eligible to enroll in the vaccination arm of cohort 2. These infants will not be randomized as they can only receive IIV. Two doses of IIV separated by 28 days will be administered to these children as they will be influenza-vaccine naïve. Infants between 3 and 12 months of age who are unvaccinated and present with influenza-like illness will be eligible to enroll in the infection arm of cohort 2.

8.4: Accountability of Investigational Supplies:

Some children will receive their first dose of influenza vaccine at the time of study enrollment in the office of their primary care physician. The clinic will be responsible for storing and maintaining these vaccines as recommended by the manufacturer. A supply of both vaccines will also be stored in a secure, limited-access, temperature monitored refrigerator at 2°C to 8°C in the VRU until needed. The temperature of the storage unit will be monitored throughout the duration of the study and documentation of proper storage will

be maintained. In the event of accidental deep-freezing or disruption of the cold chain, the vaccines will not be administered.

8.5: Subject Withdrawal of Study Drug

No medications will be chronically administered as part of this study.

8.6: Emergency Drug Disclosure:

Vaccine administration will not be blinded.

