13. DATA ANALYSIS AND MONITORING

13.1: Sample Size Determination:

	d=0.3	d=0.35	d=0.4
n1=25, n2=25	0.738	0.858	0.934
n1=30, n2=30	0.815	0.915	0.968
n1=35, n2=35	0.871	0.95	0.985
n1=30, n2=10	0.517	0.646	0.761
n1=30, n2=15	0.64	0.772	0.871
n1=30, n2=20	0.721	0.844	0.924

The primary endpoint of this study is CD4 T cell responses. Based on a study of immune response in children and adults (62), the overall mean percentage of IFN γ + CD4 T cells in 5-9 year old children vaccinated with IIV or LAIV is around 0.1%, or -3 in log₁₀ scale. The standard deviation (STD) in log₁₀ scale is around 0.4. The geometric mean differences induced by vaccinations or between the two types of vaccination is around 0.3 in log₁₀ scale. The above table summarizes statistical power based on Student's two sample *t*-test. Assuming our responses are similar, recruiting n=30 subjects in each group will give us adequate power (0.815) for Aim 1. Because LAIV is an attenuated virus, it is reasonable to assume that the difference in CD4 T cell responses induced by IIV and natural influenza infection is larger (d=0.4), therefore recruiting

n=30 subjects in the IIV group and n=15 subjects in the infection group can achieve adequate power (0.871) for Aim 2. For Aim 3, assuming that within-group STD is 0.4 and between-group STD is just 0.2, the power is 0.851 if we recruit n=105 subjects divided them into four subgroups (n1=30, n2=30, n3=30, n4=15).

13.2: Planned Statistical Analysis:

We outline the statistical analysis strategies for the specific aims as follows. **Aim 1:** A cohort of n=60 healthy children will be recruited and divided into two groups with equal sample size (n=30); one group will be vaccinated with LAIV and the other with IIV. Their T cell and antibody responses will be measured at three time points: Baseline, day 10, and day 24 post-vaccination. We will apply Shapiro-Wilk's test to check the normality. If the data passes the normality test, two sample *t*-tests will be used to detect significant mean difference between the two groups at each time point. Otherwise, Wilcoxon rank-sum test will be used. Because multiple response variables are used in this analysis, the *p*-values will be adjusted by the Benjamini-Hochberg multiple testing procedure (80) to control the false discovery rate (FDR) at the level of 0.05. In addition to pairwise comparisons, the following linear mixed effect model will be used to analyze data collected from all time points:

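### Enrolment probably spans about two influenza seasons, but no planned CD4 or antibody analysis contains season, so the non-randomised contrasts in Aims 2 and 3 are open to bias if season mix differs between groups

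*Combined protocol and SAP*

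**What the plan says.** **Timing.** Section 2.1: "It is anticipated that this study will last 3 years, with approximately 1 year of follow up for each subject". No section gives the number of enrolment seasons or an accrual rate. Vaccinated infants (cohort 2A) "will be enrolled in the fall before influenza begins to circulate in the community" (2.1). For the 15 infected infants (cohort 2B), section 3.1a says "we anticipate having to screen up to 90 children with signs of influenza like illness during the height of seasonal influenza circulation".

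**Allocation.** Cohort 1 is block randomised to LAIV or IIV, except that children with recent wheezing go to IIV (2.1, 8.3). Of the vaccinated infants, 8.3 says "These infants will not be randomized as they can only receive IIV"; the infected infants are defined by their illness.

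**Why season could matter.** Section 1.2 says that "the rapid accumulation of point mutations in both the HA and NA proteins allow this virus to drift", that IIV is made by "chemical inactivation of the H1N1, H3N2, and influenza B viral strains predicted to be circulating", and that "LAIV failed to protect against H1N1 strains in the 2013-14 influenza season". Section 8.1 allows trivalent or quadrivalent IIV.

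**Analysis (13.2).** Aim 1 uses t or Wilcoxon tests that "will be used to detect significant mean difference between the two groups at each time point". Aim 2 repeats these for 2A v 2B. Aim 3 uses one-way ANOVA or Kruskal-Wallis over four groups, with Tukey comparisons. Model (0.1), which Aims 2 and 3 cite as Equation (1.1), has group, a visit-time effect and error. Season, strain and vaccine formulation appear in none of these.

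**The concern.** The primary endpoint is the CD4 response to HA and NP peptide pools, and vaccine and circulating strains may change from year to year. A child's enrolment season may therefore shift the measured response whatever the route of priming.

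Randomisation largely protects LAIV v IIV within cohort 1. Nothing similar protects 2A v 2B, or a comparison of cohort 1 with cohort 2. The two infant groups fill by different mechanisms: 2A when families volunteer in the fall, 2B when an epidemic supplies cases. No rule keeps their season mix alike. In Aim 3 the rechallenge vaccine is that of the following fall, so it too varies with enrolment season. An unadjusted test would read any resulting difference as an effect of priming.

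**Working it through.** **Inputs from 13.1:** SD 0.4 log10; Aim 1 30 v 30, difference 0.3, power 0.815; Aim 2 30 v 15, difference 0.4, power 0.871.

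**Assumptions, because the documents give no figure:** two enrolment seasons; a season shift of 0.1 to 0.3 log10, equal in all groups; SD 0.4 within season; the second-season counts shown below; two-sided 0.05 per comparison, before FDR adjustment.

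**1. The plan's figures reproduce.**
- Aim 2: noncentrality 0.4 / (0.4 × √(1/30 + 1/15)) = 3.16 on 43 df gives 0.871.
- Aim 1: 0.3 / (0.4 × √(2/30)) = 2.90 on 58 df gives 0.815.

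**2. Bias.** Bias = shift × (season-2 share in 2B − season-2 share in 2A). With 10/30 v 11/15 the shares differ by 0.733 − 0.333 = 0.40. Shifts of 0.2 and 0.3 give bias of 0.08 and 0.12 log10, which is 20% and 30% of the planned 0.4.

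**3. Aim 2 false-positive rate of the unadjusted t-test** (100,000 simulated trials per cell):

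| Season 2: 2A v 2B | shift 0.1 | shift 0.2 | shift 0.3 |
|---|---|---|---|
| 15/30 v 8/15 | 0.048 | 0.044 | 0.037 |
| 15/30 v 10/15 | 0.052 | 0.051 | 0.050 |
| 10/30 v 8/15 | 0.051 | 0.054 | 0.059 |
| 15/30 v 11/15 | 0.052 | 0.059 | 0.066 |
| 10/30 v 11/15 | 0.059 | 0.087 | 0.124 |
| 9/30 v 12/15 | 0.065 | 0.111 | 0.182 |

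With season in the model the rate is 0.049 to 0.052 in every cell. With near-equal mix the unadjusted test is slightly conservative. If the groups share no season, a shift of 0.2 gives 0.34 and adjustment is impossible.

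**4. Aim 2 power at 0.4 with 10/30 v 11/15.** If the shift opposes the true effect, unadjusted power is 0.68 (shift 0.2) or 0.53 (shift 0.3), against about 0.82 adjusted.

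**5. Cost of adjusting.** The variance of the group estimate is multiplied by 1/(1 − r²), where r is the correlation of group with season.
- 10/30 v 11/15: r² = 0.143, factor 1.167; noncentrality 3.16/√1.167 = 2.93 on 42 df gives 0.816. This is the price if season has no effect.
- 15/30 v 8/15: factor 1.001, power 0.870.

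**6. Cohort 1, equal mix (15/30 in each arm), difference 0.3.** Unadjusted power is 0.80 (shift 0.2) or 0.78 (shift 0.3); adjusted it is about 0.81. There is no bias.

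**7. Aim 3 ANOVA false-positive rate, shifts 0.2 and 0.3** (20,000 trials; season-2 counts for three groups of 30 and one of 15):
- 15, 15, 15, 8: 0.042 and 0.029
- 15, 15, 10, 10: 0.057 and 0.062
- 10, 10, 15, 12: 0.076 and 0.111

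**The case against.** **The harm is conditional, and its inputs are assumed.** This stands. A reader might infer that enrolment has to cover two seasons and that the mix of 2A and 2B will differ. The documents say neither: single-season accrual is not excluded, and both groups could recruit in each season. A shift of 0.3 would equal the whole difference that 13.1 attributes to vaccination or vaccine type. Only a large shift together with a large imbalance matters much.

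**The biological evidence is indirect.** This also stands. The remark on LAIV in 1.2 concerns protection, not CD4 responses, and 1.2 notes that T cells can recognise conserved internal proteins. It does not show a season effect on the primary endpoint.

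**Existing provisions may cover it.** They do not. Section 10.1 mentions confounding factors but names no variable or method. Batch-effect removal in 13.2 is for RNA-seq only. The sensitivity analysis in 5.5 concerns undocumented infection.

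**One additive season term is an incomplete remedy.** Correct. For 2A season stands for the vaccine strain and for 2B the infecting virus, so the shift need not be the same. If the groups share no season, no model can separate the two effects. This limits what adjustment can claim, but it is also a reason to report season by group.

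**Adjustment might seem to raise cohort 1 power well above 0.815.** That would require treating SD 0.4 as including season there while treating it as within-season in Aim 2. On one convention, adjustment only recovers what season took away.

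**Conclusion.** The gap is real: no planned analysis of the CD4 or antibody endpoints contains season, and nothing keeps season mix alike across the non-randomised groups. The contrasts exposed to bias are 2A v 2B in Aim 2, and 2A v 2B and the cross-cohort comparisons in Aim 3. It would be wrong to call all of Aim 3 non-randomised: LAIV v IIV is randomised apart from the children with recent wheezing, and for cohort 1 the main effect is a small loss of precision.

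The consequence ranges from nothing, or slight conservatism, when mix is similar, to roughly a doubling of the Aim 2 false-positive rate at 10/30 v 11/15 with shifts of 0.2 to 0.3. Neither the shift nor the mix can be checked from the documents. The power figures in 13.1 are not in error on this point. The change is worth making because it is cheap and uses enrolment dates; it does not require showing that bias will occur.

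**What to change.** In 13.2:
- Add enrolment season as a fixed effect to the per-visit comparisons in Aims 1 and 2 (a stratified Wilcoxon test where ranks are used), to model (0.1) and its Aim 2 and Aim 3 versions, and to the Aim 3 ANOVA. If all enrolment falls in one season, the term drops out.
- Report numbers enrolled by group and season for all four groups.
- Keep the unadjusted tests as a sensitivity analysis.
- State that where two groups share little or no season, or where the season effect may differ between vaccine and infection, the group contrast cannot be separated from season.

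Optional: a new cohort 1 allocation list each season, and a descriptive display of LAIV v IIV by season. Existing blocking makes the first a small gain, and the second would have too few children per season to test.

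Cost: wording, and one degree of freedom for two seasons. Aim 2 power at 0.4 stays at 0.870 with near-equal mix, and falls from 0.871 to about 0.82 if season is unbalanced as in 10/30 v 11/15 but has no effect. The change should be fixed before outcome data are examined, since the study is open-label.

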Blood draw: A weight-based sample of whole blood will be collected by venous puncture using CPT tubes, with the blood volume determined as described in Table 1. While not required, a lidocaine 2.5% and prilocaine 2.5% anesthetic cream (EMLA cream) may be applied at the start of the study visit in order to provide local anesthetic affect. This cream will be applied in the following circumstances: 1) on parental request, 2) in the situation of high parental or child anxiety regarding the blood draw, or 3) when there is a history of a prior difficult blood draw. On collection of blood, the specimen will be centrifuged and plasma and PBMCs will be isolated within several hours of the blood being obtained (per the manufacturer's instructions, blood is stable in CPT tubes for at least 2 hours post draw). Plasma will be aliquoted into equal volumes and stored at -80°C for use in ELISA, antibody array, and microneutralization assays. PBMCs will be washed, counted, and frozen in liquid nitrogen for later use in intracellular cytokine staining, multiplex cytokine assays, RNA-seq, and CD4 T cell and memory B cell Elispot assays. If blood cannot be successfully obtained, this will be documented on the case report form as "unable to be obtained."

Nasal swab: Nasal swabs will be obtained by placing two UV-sterilized soft nylon flocked swabs into alternate nostrils of the infant and gently rotating them across the mucosa to collect respiratory secretions. One of these swabs will be used to perform a rapid influenza test in the primary care office, the VRU, or the

subject's home. The other swab will be placed into 1 mL of viral culture transport media for future RT-PCR studies.

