- The procedure to conduct blood draws and nasal wash specimens in the home setting will be the same as that used in outpatient setting (see home visit SOP). An experienced pediatric research nurse will go on all study visits to complete the blood draw. This nurse will be accompanied by either the study PI or a research assistant trained in how to hold subjects to optimize the success of blood collection. If blood is unable to be obtained, this will be documented on the Case Report Form. There will not be a requirement for the subject to present to the VRU in the event blood is unable to be collected.
- To ensure the safety of the researchers, study personnel will travel to the patient's residence in pairs. All compensation payments will be made either by Bank of America VISA Prepaid card or by check mailed to the subject after the study visit. When a Bank of America VISA card is used, the card will carry no balance on being handed to the patient. The \$25 will be added to the card by study personnel on return to the hospital following completion of the study visit. Members of the research team will be mandated reporters. In the event that potential child abuse or neglect is observed, the case will be reported to Child Protective Services as required. The consent form will

include mandatory reporting language to inform parents that the members of the research team are required to report any observed or suspected child abuse or neglect.

6. CONCOMITANT AND DISALLOWED MEDICATIONS:

There are no restrictions on the medications that can be provided during the course of the study. All medications necessary for the health and well-being of the child will be allowed. All medications used during the study will be recorded on the data collection form and updated at each study visit. No medications other than yearly seasonal influenza vaccine will be administered as part of this study.

7. SUBJECT WITHDRAWALS:

Subjects may withdraw consent for study participation at any time during the study without penalty. The subject will also be considered a study withdrawal if they are lost to follow up or are unable to comply with study procedures or visits.

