$$y_{kit} = \alpha_k + \beta_k G(i) + \gamma_{kt} + \delta_{kit}. \quad (0.1)$$

Here y_{kit} represents the k th response variable measured from the i th subject at the t th time point; α_k is the overall mean value of y_{kit} ; $G(i)$ is a binary variable which equals 0 if the i th subject is vaccinated with LAIV and 1 otherwise; β_k is a linear coefficient that quantifies the magnitude of the group-effect; γ_{kt} is a random effect term that quantifies the time effects; and δ_{kit} represents independent measurement errors. Likelihood ratio test will be used to test $H_0: \beta_k = 0$ against $H_1: \beta_k \neq 0$. **Aim 2:** Two groups of infants will be recruited for this aim. The first group (n=30) will receive a prime-boost IIV series; the other group (n=15) consists of infants who are infected by influenza naturally. Multiple clinical endpoints will be recorded at 3 time points for both groups. We will apply two sample *t*-test (or Wilcoxon rank-sum test, if Shapiro-Wilks test rejects the assumption of normality) at each time point to detect significant group differences. In addition, we will apply a linear mixed effect model similar to Equation (1.1) to detect the overall group effect. The resulting *p*-values will be properly adjusted to control for FDR at a 0.05 level. **Aim 3:** All subjects (four subgroups; n=105) will be followed longitudinally for a year and then be revaccinated with IIV. CD4 T cell responses, antibody responses, and transcriptional profile (high-throughput RNA-seq) will be measured at three time points: prior to IIV re-vaccination, d10 and 24 days post re-vaccination. We will apply one-way ANOVA *F*-test (or Kruskal-Wallis test, if the normality assumption is rejected) to detect significant group differences at each time point. Post-hoc analysis based on Tukey's adjustment will be used to test for significant differences between groups. We will also apply a linear mixed effect model similar to Equation (1.1) to detect the overall group effect. For high-throughput transcriptional data, first we will apply suitable pre-processing techniques such as non-specific filtering (81), normalization (82) and batch-effect removing

(83). We then select differentially expressed genes at each time point by specialized procedures such as DEseq (84) and DEGseq (85). Benjamini-Hochberg procedure will be used to control FDR at a 0.05 level for all analyses.

13.3: Data and Safety Monitoring:

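### Equation (0.1), a supplementary mixed model, pools three visits per child with no within-child term, so its test of the overall group effect is anti-conservative when within-child covariances sum to more than zero

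*Combined protocol and SAP*

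**What the plan says.** Section 13.2 (Aim 1) states that T cell and "antibody responses will be measured at three time points: Baseline, day 10, and day 24 post-vaccination". The groups are compared at each visit by a two-sample t-test, or by a Wilcoxon rank-sum test if normality is rejected. The model then comes as a supplement: "In addition to pairwise comparisons, the following linear mixed effect model will be used to analyze data collected from all time points".

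The model is y_kit = α_k + β_k G(i) + γ_kt + δ_kit, for response k, child i and time t. The plan defines each term in words. G(i) is a binary group indicator. γ_kt "is a random effect term that quantifies the time effects". δ_kit "represents independent measurement errors". A likelihood ratio test of β_k = 0 is planned.

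For Aim 2: "In addition, we will apply a linear mixed effect model similar to Equation (1.1) to detect the overall group effect". For Aim 3: "We will also apply a linear mixed effect model similar to Equation (1.1) to detect the overall group effect". The printed equation is numbered (0.1), not (1.1). The random structure for Aims 2 and 3, and the coding of the four groups in Aim 3, are not stated.

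No other section adds a child random effect, a within-child covariance or a robust variance.

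**The concern.** The random term carries the indices k and t but not i, so it absorbs shifts shared by all children at a visit. It does not represent the tendency of one child to run high or low at every visit. With independent errors on top, 60 children at three visits enter the Aim 1 test as 180 independent observations. Group is a between-child factor, so the standard error of β_k is too small if a child's values are positively correlated overall.

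Two things are at stake. First, the overall group effect would be declared too often. The Benjamini-Hochberg step does not repair this, because it needs p-values that are valid on entry. Second, this model is the only planned analysis that uses all visits together, and the plan does not say which result prevails if it disagrees with the per-visit tests.

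**Working it through.** **Inputs from the documents (sections 13.1 and 13.2).** Three visits per child. Groups of 30 v 30 (Aim 1), 30 v 15 (Aim 2) and 30, 30, 30, 15 (Aim 3). SD 0.4 on the log10 scale. Differences of 0.3 (Aim 1) and 0.4 (Aim 2). **Assumed, because the documents do not give it:** the within-child correlation ρ.

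**1. The plan's own power figures.** Noncentral t, two-sided 5%, SD 0.4: 30 v 30 with d = 0.3 gives 0.815, and 30 v 15 with d = 0.4 gives 0.871. Both match section 13.1. They use one value per child, so the defect does not touch them.

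**2. Variance ratio.** Let S be the 3×3 within-child covariance matrix. With complete data and a common S:

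- true variance of the β_k estimate = (1/n1 + 1/n2) × (sum of all entries of S)/9
- variance under Equation (0.1) = (1/n1 + 1/n2) × (sum of the three variances)/9
- ratio = 1 + 2 × (sum of the three covariances)/(sum of the three variances)

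The ratio exceeds 1 exactly when the covariances sum to more than zero. With equal variances and a common ρ it is 1 + 2ρ.

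**3. Type I error at nominal 5%.** Two groups: 2 × [1 − Φ(1.96/√ratio)]. Four groups, if Aim 3 uses three group indicators and the same random structure: P(χ² on 3 df > 7.815/ratio).

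| ρ | ratio | two groups | Aim 3 |
|---|---|---|---|
| 0.1 | 1.2 | 0.074 | 0.089 |
| 0.3 | 1.6 | 0.121 | 0.180 |
| 0.5 | 2.0 | 0.166 | 0.272 |
| 0.7 | 2.4 | 0.206 | 0.354 |
| 0.9 | 2.8 | 0.241 | 0.425 |

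Example: at ρ = 0.5, 1.96/√2 = 1.386 and the two-sided tail is 0.166.

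Simulating the printed likelihood ratio test (40,000 replicates per setting) gives, in the same order of ρ, 0.075, 0.121, 0.168, 0.209, 0.247 for Aim 1 and 0.093, 0.181, 0.279, 0.360, 0.438 for Aim 3. At ρ = 0, Aim 1 gives 0.050, so the missing term is the cause.

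**4. A weaker pattern.** If only days 10 and 24 are correlated, at 0.5, the ratio is 1 + 2 × 0.5/3 = 1.333 and the two-group size is 0.090.

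**5. Where the threshold moves.** Aim 2, ρ = 0.1, group variances unequal (units arbitrary):

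- Larger group has twice the variance. The entries of S sum to 2 × 3 × 1.2 = 7.2 and 3.6. True variance = 7.2/(9×30) + 3.6/(9×15) = 0.0533. Pooled variance = (30×2 + 15×1)/45 = 1.667, so the model variance = (1.667/3) × (1/30 + 1/15) = 0.0556. Ratio 0.96, size about 0.045.
- Smaller group has twice the variance. True variance = 3.6/(9×30) + 7.2/(9×15) = 0.0667. Pooled variance = (30 + 30)/45 = 1.333, model variance 0.0444. Ratio 1.5, size about 0.11.

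With 30 v 30 the group sizes are equal, so Aim 1 does not have this problem.

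**6. Does a within-child term repair it?** With complete data, the three-visit group effect can be tested by a t-test or ANOVA on each child's mean. With visit SDs 0.3/0.5/0.4 and ρ of 0.1, 0.5 and 0.9 (20,000 replicates), the size is 0.047 to 0.052 over the three aims.

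**The case against.** **The model is only supplementary.** This stands. The per-visit t, Wilcoxon, ANOVA and Kruskal-Wallis tests use one value per child and are valid in this respect. A reader might infer that the trial's main comparisons or its sample size are compromised. The documents do not support that: section 13.1 bases power for Aims 1 and 2 on the two-sample t-test.

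**A child effect was probably intended.** Possibly, since the plan calls it a mixed model. But every term is defined in words and none is for the child, so an analyst who follows the text fits the faulty model. If a child effect was meant, the correction records it.

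**The inflation is not universal.** This stands. A reader might infer that the p-values are too small whenever values correlate positively within a child. That needs equal group sizes or a covariance common to the groups, and in Aim 2 the size can fall slightly below 5% (step 5). If the covariances sum to less than zero, the test is conservative.

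**The baseline visit should be dropped from the overall effect.** A reader might go on to argue this, because a pre-vaccination visit dilutes a response effect in Aim 1. The dilution is real. With differences of 0, 0.3 and 0.3 at the three visits, the average is 0.20 rather than 0.30, and at SD 0.4 and ρ = 0.5 a valid test has power 0.645 over three visits against 0.910 over days 10 and 24. But this is a different estimand, not a repair of the error. Section 2.2 expects CD4 responses to contract by day 24, and if the day-24 difference is 0 the two-visit contrast has power 0.378, below the 0.815 of the planned day-10 t-test. In Aim 3 the pre-revaccination visit may itself carry priming differences.

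**Conclusion.** Equation (0.1) is wrong as written for Aim 1. For Aims 2 and 3 the same fault is inferred from the word similar; to call it established there would go beyond the text.

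Under complete data, and equal group sizes or a common covariance, the size of the overall test at nominal 5% runs from about 0.074 to 0.241 for two groups as ρ goes from 0.1 to 0.9. For Aim 3 it runs from 0.089 to 0.425, which also assumes three group indicators and the same random structure. The direction for Aim 1 follows from algebra once the covariances sum to more than zero. The amount depends on a correlation that the documents do not give, and the upper rows are a worst case.

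This should be fixed before analysis. It affects the overall-effect p-values only.

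**What to change.** **Required.** In all three aims, add a within-child term to Equation (0.1): either a child random intercept or an unstructured within-child covariance. Make time a fixed effect, and test the plan's group effect in that model. State the group coding for Aims 2 and 3, and correct the equation number. With complete data, a t-test or ANOVA on each child's three-visit mean is a valid equivalent.

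**Optional, not part of the error.**

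- Unstructured covariance with REML and a Kenward-Roger correction. This is useful if visits are missing, or if a group-by-time contrast is tested with unequal visit variances. Failed draws are foreseen in section 5.2 ("If blood cannot be successfully obtained, this will be documented on the case report form as" unable to be obtained). For home visits, section 5.11 adds: "There will not be a requirement for the subject to present to the VRU in the event blood is unable to be collected".
- For Aim 1, an added and labelled post-vaccination contrast over days 10 and 24. It changes the estimand, so it should not replace the plan's overall effect, least of all in Aim 3.

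**Cost.** SAP wording and slightly more analysis. No new data, visits or children, and the sample size is unchanged. Overall-effect p-values become larger where they were falsely small.
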